### **8.2. Informed Consent**

At the first screening visit, candidates will meet with either the site PI or his/her designee and receive an explanation of the study purpose and requirements. If still interested after receiving an explanation of the study, the candidate will be given an opportunity to review, inquire about, and sign the study informed consent form approved by the IRB. Subjects will be given a copy of the signed informed consent form. All subjects who sign informed consent must be registered in the electronic data management system (EDMS) as enrolled in the study. The EDMS will assign the subject a unique subject ID number that will be used on all of the data collection forms and electronic system entries.

### **8.3. Selection and Withdrawal of Subjects**

#### **8.3.1. Inclusion Criteria**

Subjects must meet each one of the following inclusion criteria in order to be eligible for participation in the study:

1. Healthy male or female volunteer, ages 18-to-55 years, inclusive.
2. BMI must be between 18 and 32 kg/m^2 (inclusive) and weigh a minimum of 50 kg (110 lbs). BMI is calculated as weight in kg divided by the square of height measured in meters.
3. A condition of general good health, based upon the results of a medical history, physical examination, vital signs, laboratory profile, and a 12-lead electrocardiogram (ECG).
4. If female, be postmenopausal (at least 2 years prior to dosing), surgically sterile (6 months post tubal ligation), or agree to use an acceptable form of birth control from screening until 28 days after dosing. Subjects who claim postmenopausal status will have

status confirmed with a follicle-stimulating hormone (FSH) test. Acceptable forms of birth control for females include the following:

- Vasectomized partner (at least 6 months prior to dosing)
  - Surgical sterilization (bilateral tubal ligation, hysterectomy, bilateral oophorectomy) at least 6 months prior to dosing
  - Non-surgical permanent sterilization (eg, Essure procedure) at least 3 months prior to dosing
  - Double barrier (diaphragm with spermicide; condoms with spermicide)
  - Nonhormonal intrauterine device
  - Abstinence (must agree to use a double barrier method if they become sexually active during the study)
5. If male, agree to use an acceptable method of birth control during the study and 90 days following dosing. Acceptable forms of birth control for males include the following:
- Vasectomy (at least 6 months before dosing)
  - Partner is surgically sterilized (see methods above for females)
  - Partner uses oral, injectable, or implantable hormonal contraceptives or intrauterine device (IUD)
  - Double barrier (partner uses diaphragm with spermicide; condoms with spermicide)
  - Abstinence (subject must agree to use a double barrier method if subject becomes sexually active during the study)
6. If female, agree to not breastfeed or donate ova from the time of consenting to the study and for 28 days after dosing the study drug.
7. If male, agree to not donate sperm from the time of consenting to the study and for 90 days after dosing the study drug.
8. Be able to verbalize an understanding of the consent form, able to provide written informed consent, verbalize willingness to complete study procedures, able to understand written and oral instructions in English.
9. Complete all assessments required at screening and baseline and be available to stay in the Phase I unit for a period of approximately 4 days and 3 nights and return for a follow-up visit.
10. Provide contact information of someone, such as a family member, spouse, or significant other, who may be able to contact the subject in case of a missed clinic appointment.
11. Be someone who in the opinion of the investigator would be expected to complete the study protocol.

### 8.3.2. Exclusion Criteria

Subjects will not be eligible to participate in this study if any one of the following exclusion criteria is met:

1. History of significant sensitivity to any drug.
2. Requirement for any over-the-counter and/or prescription medication, vitamins and/or herbal supplements (including cannabis and cannabis derived products, including CBD-containing products) on a regular basis or use of any of the above within 14-day period prior to clinical intake and agree to not use any of these medications for the duration of the study.
3. More than moderate alcohol consumption in the past 8 weeks. Moderate alcohol consumption is defined as limiting intake to 2 drinks or less in a day for men and 1 drink or less per day for women. Examples of one drink include: Beer: 12 fluid ounces (355 milliliters); Wine: 5 fluid ounces (148 milliliters); Distilled spirits (80 proof): 1.5 fluid ounces (44 milliliters).
4. Has a clinically significant laboratory test that is out of range of normal limits. An out of range of normal limit laboratory value is clinically significant if associated with one of the following: a) clinical diagnosis; b) systemic signs and symptoms; c) physical exam finding; d) more than 20% above the upper or below the lower limit of normal (for CPK, 1.5 times the upper limit of normal and based on the subject's medical history).
5. Have a urine toxicology screen positive during screening or baseline for any of the following substances:
  - a. ethylglucuronide (alcohol metabolite),
  - b. amphetamines,
  - c. barbiturates,
  - d. benzodiazepines,
  - e. buprenorphine,
  - f. cocaine,
  - g. fentanyl,
  - h. methylenedioxymethamphetamine (MDMA),
  - i. methadone,
  - j. methamphetamines,
  - k. morphine,
  - l. opioids,
  - m. oxycodone,
  - n. phencyclidine and/or
  - o. tetrahydrocannabinol (THC)
6. If female, positive pregnancy test or nursing.
7. Positive test result for hepatitis A virus immunoglobulin M (HAV-IgM), hepatitis B surface antigen (HBsAg), or hepatitis C virus antibody (HCV Ab) or HIV antibodies (HIV Ab). Negative HIV status will be confirmed at Screening, and the results will be maintained confidentially by the study site.

8. Positive SARS-CoV-2 antigen test prior to 72 hours of clinic intake.
9. History of any clinically significant cardiac, respiratory, renal, hepatic, gastrointestinal, hematologic, endocrine, dermatological, metabolic, neurological (nerve injury) or psychiatric disease or disorder, or any uncontrolled medical illness.
10. History of gastroesophageal reflux disease, gastrointestinal ulcers, gastrointestinal bleeding, inflammatory bowel disease or gastroesophageal surgery.
11. Use of any known strong CYP3A4 inhibitors (e.g., ketoconazole) or dual CYP3A4 and 2C9 inhibitor (eg. Fluconazole), or dual CYP3A4 and 2C9 inducer (eg. Rifampin), or use of any monoamine oxidase inhibitors (MAOIs) within 1 month prior to study drug administration.
12. Receipt of any drug by injection within 30 days prior to study drug administration.
13. History of head trauma with loss of consciousness, history of epilepsy, seizures or convulsions, including febrile, alcohol, or drug withdrawal seizures.
14. A clinically notable vital sign abnormality including a history of syncopal or near syncopal events following abrupt change in posture.
15. Have any of the following at screening or baseline:
  - Blood pressure: systolic > 140 mmHg, diastolic > 90 mmHg at Screening or Day -1.
  - Heart rate: > 100 beats/minute at screening or Day -1
16. History of cardiovascular abnormality, including left ventricular dysfunction, sick sinus syndrome, family history of long-QT syndrome, or unexplained sudden deaths in their family.
17. Has a clinically significant abnormal ECG or an ECG with a QTc interval corrected for heart rate using the Fridericia formula (QTcF) > 430 msec.
18. History of gastric surgery, vagotomy, bowel resection, or any surgical procedure that might interfere with gastrointestinal motility, pH, or absorption.
19. Has an estimated creatinine clearance (CrCl) outside of normal range.
20. Donation or loss of 550 mL or more blood volume (including plasmapheresis) or receipt of a transfusion of any blood product within 8 weeks prior to study drug administration.
21. Receipt of any investigational product within 6 weeks prior to study drug administration.
22. Consumption of alcohol within the 1-day period prior to study drug administration.
23. Consumption of grapefruit or grapefruit products from 3 days prior to study drug administration to study drug administration.
24. Use of tobacco or nicotine-containing products within the 6-month period preceding study drug administration.
25. Current enrollment in another clinical study.
26. Previous enrollment in this study.

27. Consideration by the investigator, for any reason, that the subject is an unsuitable candidate to receive kindolor tosylate.

#### **8.4. Eligibility Screening**

After the subject signs informed consent, screening may begin. During the first screening visit, subjects will undergo the following assessments:

- Demographics
- Medical/Surgical History
- Physical Examination
- Height/Weight
- 12-Lead ECG
- Vital Signs
- Clinical laboratory tests including chemistry, hematology, amylase, lipase, coagulation, urinalysis, infectious diseases, Urine Drug/Alcohol Screen, and Pregnancy Test
- SARS-Cov-2 Antigen Test (must be obtained within 72 hours of clinic intake)
- Birth control methods for men and women
- Prior and Concomitant medications

Assessments can be performed in any order except that it is recommended to take vital signs prior to blood draws. If any of these assessments reveal that the subject is not eligible for the study, screening can be immediately terminated, and no further data be collected. Clinical laboratory tests may be repeated at the discretion of the investigator if the first assessment yields values outside normal laboratory limits.

After all screening assessments are completed and if the subject is still considered eligible, they will be instructed not to take any new medications, or they may not be able to participate in the study and will be instructed to continue to use an appropriate method of birth control. The subject will be provided with Hemoccult blood test supplies for FOBT and with instructions to collect a stool specimen at home and to mail back the sample to the clinic for microscopy. Females should not take the test during their period as menstrual blood may end up in the sample leading to a false positive. The instructions will include the following dietary restrictions:

Starting 3 days before you begin collecting your stool samples, avoid:

- Red meat, such as beef, lamb, or liver
- Raw fruits and vegetables
- Vitamin C, such as fruit juices with vitamin C and vitamin C supplements in doses higher than 250 mg per day
- Antacids (medications to relieve heartburn or stomach pain, such as Tums®)
- Medications to stop diarrhea (loose or watery bowel movements)

- Iron supplements

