Eligible subjects will undergo intake procedures at the UCSD Clinical and Translational Research Institute Phase I unit on Study Day -1 (the day before starting dosing) and will complete final screening and baseline evaluations. On Study Day 1, subjects will receive the study drug after an overnight fast (about 8 hours) with no food allowed until 4 hours after dosing. Study drug tablets will be administered with 240 mL of water. Water will be allowed anytime except for one hour before and after dosing. Subjects will remain in the unit for at least an additional 48-hours for safety assessments and blood collections to determine plasma levels of kindolor. Pre-dose assessments will be conducted prior to administration of study drug on Study Day 1. Blood for PK analysis will be collected ~ 15 minutes prior to dosing, then at 0.25, 0.5, 1, 1.5, 2, 4, 8, 12, 24, and 48 hours after dosing. Safety will be assessed by collecting adverse events (AEs), vital signs, physical examination, ECG, FOBT, Stool Consistency Questionnaire, GI Signs and Symptoms Checklist, urine output (24 hours) and clinical laboratory tests (amylase, lipase, chemistry, hematology, coagulation tests, pregnancy tests, and urinalysis). AEs will be assessed daily after the start of dosing, with closer evaluations in the 4-hour period after the start of dosing. Sitting (3 minutes) vital signs will be taken during screening, at clinic check in, pre-dose, then at 15, 30, 60 minutes and 2, 4, 6, 12, 24, and 48 hours post dose. A 12-lead ECG will be obtained prior to dosing, then at 2, 6, 12, 24, and 48 hours post dose. When vital signs or ECG are scheduled at the same time as a PK blood draw, these assessments will be performed before drawing any blood. The FOBT will be performed at screening, clinic intake on Day -1, pre-discharge on Day 3, and at follow-up on Day 7. Subjects will return for a final follow-up visit 7 ± 2 days after discharge for a final safety assessment including ECG, vital signs, AEs, FOBT Stool Consistency Questionnaire, GI Symptoms Checklist, and clinical laboratory tests. Males will be contacted 90 days and females 28 days after study drug administration to verify continued contraceptive use and having not donated sperm for males and have not breast fed a baby or donated ova for females during this period. The study schedule of visits and assessments is shown in [Table 6](#).

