#### **8.6.1. Confinement**

Subjects will be confined to the study site and supervised over a 4-day period starting on Study Day -1. Confinement will conclude after the scheduled study procedures are completed on Study Day 3. Strenuous activity during confinement will not be permitted.

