#### **8.6.2. Meals, Dietary Requirements, and Other Restrictions**

Subjects will receive a standardized diet, providing approximately 30% of the daily calories from fat, for all meals during confinement. Subjects will start fasting on Study Day -1 after the evening meal and should be fasting for about 8 hours with no food allowed until 4 hours after dosing on Day 1. Starting with lunch on Study Day 1 until after the 24-hour blood collection on Study Day 3, the subjects will consume only the scheduled meals provided in the study and water to quench thirst. The subjects will abstain from all other food and beverage.

On the morning of dosing, non-caffeinated and nondairy liquids are permitted prior to dosing, but food is prohibited. No food or beverage, except for water to quench thirst, will be allowed on Study Day 1 from study drug dosing until after the collection of the 4-hour blood sample.

On Study Day 1 subjects will be served lunch following the 4-hour blood collection. The composition (protein, fat, carbohydrate, and total calories) of this meal will be determined by a dietician and a record will be kept with the source documents. The sequence of starting meals on the dosing days will be maintained such that the time intervals between dosing and meals are essentially the same for all subjects in each period. Subjects may not consume:

- Red meat, such as beef, lamb, or liver or raw fruits and vegetables,
- Alcohol within the 2-day period prior to any study drug administration,
- Grapefruit or grapefruit products during the study, or
- Caffeine during confinement.

Kindolor shows phototoxic potential, therefore, subjects will not be exposed to sunlight while in the Phase 1 unit and will be cautioned to limit exposure to direct sunlight after release and to apply a sun protectant lotion to exposed areas of the skin after release for at least another 24 hours.

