### **8.13.2. Dose Continuation, Dose Escalation and Study Stopping Criteria**

Continuation of dosing within a cohort, or dose escalation to sequential cohorts will stop when either:

- a) The highest dose is reached or,
- b) Clinical/laboratory/AE findings meet any of the following stopping criteria:
  - i. Two or more subjects on active medication have clinical laboratory values meeting the criteria of moderate (Grade 2) intensity
  - ii. Two or more subjects on active medication experience moderate AEs of the same type (within the same MedDRA SOC)
  - iii. One or more subjects on active medication experiences any clinical laboratory value meeting the criteria of severe (Grade 3 or 4) intensity or an AE is determined to be severe in intensity
  - iiii. Any subject has a positive FOBT
- c) The mean kindolor systemic exposure levels exceed  $AUC(T_{last})=87,550$  ng.h/mL or  $C_{max} > 13,490$  ng/mL in a single subject in a cohort.
- d) The DSMB recommends stopping escalation after review of all the data from each cohort.

The maximum tolerated dose (MTD) will be considered the highest dose where no active medication subjects meet the study stopping criteria.

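### The menses warning for the fecal occult blood test is given only with the screening kit, and diet before the follow-up sample is unclear, yet one positive test can stop the trial or set the MTD

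*Protocol*

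**What the plan says.** **Collection conditions.** Protocol 8.4 describes the Hemoccult kit handed out at screening for home collection and mailing. With it come the menses instruction, "Females should not take the test during their period as menstrual blood may end up in the sample leading to a false positive", and a diet list that opens "Starting 3 days before you begin collecting your stool samples, avoid". The list covers red meat, raw produce, vitamin C (juices and higher-dose supplements), antacids, antidiarrheals and iron.

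**Schedule.** Section 5 states: "The FOBT will be performed at screening, clinic intake on Day -1, pre-discharge on Day 3, and at follow-up on Day 7". Section 11.7 lets another sample stand in only when the Day -1 sample cannot be obtained. The schedule of assessments gives the follow-up visit as Day 7±2. Section 8.8 counts the 7±2 days from dosing, while the synopsis, Section 5 and 8.12 count them from discharge.

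**Diet after screening.** Section 8.6.1 says "Subjects will be confined to the study site and supervised over a 4-day period starting on Study Day -1". Under 8.6.2, from Day 1 lunch, "the subjects will consume only the scheduled meals provided in the study and water to quench thirst". The same section bars "Red meat, such as beef, lamb, or liver or raw fruits and vegetables" with no start or end date, although neighbouring items are limited to the study, to confinement or to a pre-dose period. Exclusion 2 requires that subjects "agree to not use any of these medications for the duration of the study", which reaches over-the-counter products, vitamins and supplements.

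**Consequence.** Criterion b.iiii of 8.13.2 reads "Any subject has a positive FOBT". Section 11.1.5 stops the study if erosion, ulcer or bleeding is confirmed by endoscopy or by FOBT. Section 8.13.2 then defines the MTD as the highest dose at which no active subject meets the stopping criteria. SAP 9.7 reports FOBT as change from baseline, and the SAP Table 20 shell has an Invalid row for FOBT that no text defines.

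**The concern.** The protocol identifies a non-gastrointestinal source of blood that can turn the FOBT positive. It guards against it at screening, where a wrong result costs little, and is silent on it after dosing, where one positive is decisive. Gastric injury is the expected toxicity, and FOBT is a scheduled objective marker for it. A menstrual positive in any woman after dosing meets a stopping criterion. In a woman on active drug it also takes that dose out of consideration as the MTD, which is part of the primary objective. The eCRF content described for FOBT includes neither menstrual status nor diet, so the cause could not be reliably reconstructed afterwards. Collection conditions may also differ between the baseline and post-dose samples that the SAP compares.

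The population makes the exposure plausible. Women aged 18 to 55 are eligible and recruitment includes an undergraduate campus. Hormonal contraception is not among the methods accepted for women in 8.3.1, and regular medication is excluded, so premenopausal participants with a uterus will mostly have natural cycles.

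**Working it through.** **Step 1: where each condition applies.**

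| Sample | Menses instruction | Red meat, raw produce | Dietary vitamin C | Medicines, supplements |
|---|---|---|---|---|
| Screening (home) | Yes, 8.4 | Yes, 8.4 | Yes, 8.4 | Yes, 8.4 |
| Day -1 | Not stated | 8.6.2 item, start not stated | Not stated | Exclusion 2 |
| Day 3 | Not stated | Study meals and 8.6.2 ban | Study meals from Day 1 lunch | Exclusion 2 |
| Follow-up (outpatient) | Not stated | 8.6.2 item, end not stated | Not stated | Exclusion 2 |

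Sections 8.5, 8.6.2, 8.8, 11.1.5 and 11.7, Appendix B and the SAP were checked for the menses instruction. None contains it. The repeat-test rule in 11.3 concerns laboratory values outside a reference range. FOBT is not in that section's table, so a repeat is not clearly provided.

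**Step 2: the plan's own figure.** The only probability in the documents is the chance of at least one AE among 6 active subjects, 1 − (1 − p)^6. At p = 10%, 15%, 20% and 25% this gives 46.9%, 62.3%, 73.8% and 82.2%, matching the stated 47%, 62%, 74% and 82%. The documents give no comparable figure for a false FOBT.

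**Step 3: scale of the menstrual route.** Inputs from the documents are 8 subjects per cohort and two post-dose samples, taken here as Day 3 and Day 7 (4 days apart). The following are assumptions: a 28-day cycle with random phase, menses of d = 4 to 6 days, w = 2 to 4 cycling women per cohort, and probability g = 10% to 50% that a sample taken during menses is positive.

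Of the 28 cycle phases, d − 4 place both samples in menses and 2d − 2(d − 4) = 8 place exactly one. Per woman:

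p = [8g + (d − 4)(1 − (1 − g)²)] / 28

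Per cohort: 1 − (1 − p)^w.

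- Low end (w = 2, d = 4, g = 0.10): p = 0.8/28 = 0.0286, and 1 − 0.9714² = 5.6%.
- High end (w = 4, d = 6, g = 0.50): p = (4 + 2 × 0.75)/28 = 0.1964, and 1 − 0.8036⁴ = 58.3%.

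**Step 4: two sensitivities.**

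- *Follow-up timing.* If the visit is 7 days after a Day 3 discharge, the samples are 7 days apart and no menses of 4 to 6 days covers both, so p = 2dg/28. The low end stays at 5.6%. The high end is p = 6/28 = 0.2143, and 1 − 0.7857⁴ = 61.9%. The timing conflict barely moves the range.
- *Active subjects only, for the MTD.* With 6 of 8 on active drug, use 0.75p per woman and treat allocations as independent. The low end is 1 − (1 − 0.0214)² = 4.2%. The high end is 1 − (1 − 0.1473)⁴ = 47.1%.

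**The case against.** Several points on the other side are sound.

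- *Diet.* A reader might infer that the whole set of collection conditions exists only for the screening sample. The documents do not support that. Confinement, study meals and the 8.6.2 ban largely close the dietary route before Day 3, and exclusion 2 covers antacids, antidiarrheals, iron and vitamin supplements for the whole study. What remains is mainly red meat, raw produce and dietary vitamin C before the follow-up sample.
- *Strength of the 8.4 wording.* It says menstrual blood may cause a false positive. It does not declare the test invalid during menses, and a reader should not infer that such results cannot measure GI bleeding. Its wording is also general, so restricting it to screening rests on where it is placed. That placement, together with silence everywhere else, is still the gap.
- *Fixed days.* The follow-up visit has a ±2-day window, which gives some room. Day 3 has none, and nothing tells staff to use the follow-up window for this purpose.
- *Intervening review.* A GI sign or positive FOBT brings in the gastroenterologist, with endoscopy if warranted. The Medical Monitor advises on whether criteria are met, and the DSMB convenes ad hoc. A reader might infer that every menstrual positive would end the trial, which skips these steps. However, b.iiii and 11.1.5 are categorical, and neither says that an explained positive can be set aside.
- *Caution.* In a first-in-human trial with a gastric signal, a trigger that errs toward stopping is defensible. That defends the rule's sensitivity but does not justify leaving a named confounder unrecorded.

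**Conclusion.** The concern holds in this form. The menses instruction is stated for the screening kit and applied to no later FOBT. The 3-day diet conditions are not clearly applied before the outpatient follow-up sample. One positive FOBT meets a stopping criterion that also governs the MTD. Followed as written, the plan can reach a stop or an MTD on a result whose false-positive cause the protocol itself describes.

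The size is uncertain. About 6% to 58% per cohort follows from assumed numbers of cycling women, days of menses and positivity, none of which the documents give. The width of that range is itself a finding. A reader might prefer a single central figure, such as the 31% per cohort obtained with 4 women, 5-day menses and 25% positivity. That rests on an unsourced positivity rate and on the top of the assumed range of women, since 8.7.1 seeks gender balance only as far as possible and postmenopausal or surgically sterile women are eligible. The range shows that the route is not negligible and supports no more precise claim. The change should be made because it is cheap and the consequence is large.

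**What to change.** 1. In Protocol 11.7 and the schedule of assessments (captioned Table 5), state that the 8.4 collection instructions on menses and diet apply to every FOBT. Repeat them to subjects at discharge.
2. Record menstrual status and diet adherence on the FOBT eCRF at each sample.
3. In the SAP, define the Invalid row of Table 20 and show results from samples taken outside the collection conditions separately from the others.
4. Reconcile 8.4, 8.6.2, 11.7, 8.13.2 b.iiii and 11.1.5 on how a sample taken outside those conditions is handled and whether it counts toward the stopping criteria. Give the red-meat and raw-produce item in 8.6.2 a stated period. The clinical rule is for the sponsor to set, and none is proposed here.
5. Reconcile the follow-up timing, which is counted from dosing in 8.8 and from discharge in the synopsis, Section 5 and 8.12.

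The cost is protocol and SAP wording, one more instruction sheet and two eCRF fields, with slightly more data collection at each visit.
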